4.6 Pharmacokinetic Endpoints

Blood samples are collected at pre-dose 0 hr and post-dose time points at 15 min, 30 min, 1 hr, 1.5 hr, 2 hr, 2.5 hr, 3 hr, 4 hr, 6 hr, 8 hr, 12 hr, and 24 hr on Day 1 and Day 5. To assess the PK profile of ATL001 after administration of multiple doses, the following PK parameters will be calculated using non-compartmental analysis (NCA) method with Phoenix® WinNonlin® software (Version 8.1 or higher, Certara, L.P.).

| Parameter | Definition |
|---|---|
| Day 1 (Initial Dose) | |
| C_{max} | Maximum observed plasma ATL-001 concentration, determined directly from individual concentration-time data |
| t_{max} | Time until C_{max} is reached, determined directly from individual concentration-time data |
| AUC_{0-last} | Area under the plasma ATL-001 concentration-time curve from time 0 to the time of the last detectable concentration after the initial dose, before the next dose administration |
| AUC_{0-12} | Area under the plasma ATL-001 concentration-time curve from time 0 to 12 hours after the initial dose |
| AUC_{0-24} | Area under the plasma ATL-001 concentration-time curve from time 0 to 24 hours after the initial dose |
| Day 5 (Steady State after Multiple Doses) | |
| C_{max-ss} | C_{max} at steady state |
| T_{max-ss} | T_{max} at steady state |
| C_{min-ss} | C_{min} at steady state |
| AUC_{τ} | Area under the plasma ATL-001 concentration-time curve during one dosing interval at steady state |
| $AUC_{0-last,ss}$ | Area under the plasma ATL-001 concentration-time curve from time 0 to the time of the last detectable concentration at steady state |
| $t_{1/2}$ | Apparent terminal elimination half-life at steady state |
| CL_{ss}/F | Apparent systemic clearance at steady state |
| V_{ss}/F | Apparent volume of distribution at steady state |
| $R_{ac}(AUC)$ | Accumulation ratio based on AUC, defined as AUC_{τ}/AUC_{0-24} |
| $R_{ac}(C_{max})$ | Accumulation ratio based on C_{max} , defined as C_{max-ss}/C_{max} |

4.7 Other Derived Variables

In the case that more derived variables than the ones described in this document are required for the analysis, they will be defined and described in the statistical report.

5. GENERAL STATISTICAL METHODS

5.1 Sample Size

The study will consist of five sequentially recruited cohorts of 8 subjects each, resulting in up to 40 randomized subjects.

No technical sample size calculation was done. This sample size of 8 subjects per cohort with a randomization 3:1 for active/placebo treatment, is regarded sufficient to demonstrate the effects of the study drug under investigation and therefore to be sufficient to fulfil the objectives of the study.

In case of a withdrawn subject from the study during the treatment period and for other reasons than safety, he/she may be replaced with another subject, at the Sponsor's discretion.

5.2 Statistical Hypotheses

No formal statistical hypothesis of the safety or tolerability will be tested for this study.

5.3 Subject's Disposition

For subject study status, the number and percentage of subjects for each one of the following categories will be presented.

- Screened subjects, including screened failures (number only).
- Screened-failure subjects (number only).
- Subjects enrolled.
- Subjects in the safety population.
- Subjects included in the PK population.
- Subjects completing treatment.
- Subjects who discontinued treatment by primary reason.
- Subjects completing the study per protocol.
- Subjects who discontinued study by primary reason.

For all categories of subjects, percentages will be calculated using the number of safety population subjects.

The subject disposition will be listed by subject (Screening population).

5.3.1 Protocol Deviations

All protocol deviations will be collected separately from the clinical database.

They will be recorded and categorized by the study monitors in Simple Trials. The PDs management will be done according to the Protocol Deviation Plan.

A listing of all patients with protocol deviations will be maintained by regional Clinical PM and periodically reviewed by the Global PM and Sponsor. The Sponsor may upgrade or downgrade the category of the protocol deviation, always based on the approved Protocol Deviation Plan.

The final list of protocol deviations will be reviewed before the database lock and provided to the biostatistician.

All protocol deviations will be listed by category and deviation type.

5.4 Summary of Statistical Methods

All subjects entered in the database will be included in subject data listings.

All relevant subject data will be included in listings.

The listings will be sorted by placebo/ dose-level cohort, subject, visit, and timepoint where applicable, unless specified otherwise.

All applicable data will be summarized overall. In addition, data will be summarized by visit and/or timepoint when appropriate. Unscheduled or repeat assessments will not be included in summary tables but will be included in listings, if any.

Continuous variables will be summarized using the number of observations (n), missing, mean, standard deviation (SD), median, Q1, Q3, minimum, and maximum along with the total number of subjects contributing values.

Descriptive statistics for categorical/qualitative data will include frequency counts and percentages. The total number of subjects in the cohort (N) will be used as the denominator for percent calculations unless stated otherwise in the table footnote.

Results of statistical analysis will be interpreted descriptively by placebo/ dose-level cohort.

No adjustment for covariates is planned for this study.

No missing value imputation will be done (except for what is included in the missing data imputation section [5.4.8](#))

All analyses will be conducted on observed data.

5.4.1 Demographics, Other Characteristics, Prior, and Concomitant Medication

5.4.1.1 Demographic and Other Characteristics

The following variables for demographics characteristics will be summarized by placebo/ dose-level cohort and overall:

- Age (years) / Age range (< 65, [65,85], > 85).
- Gender (Male / Female / Unknown / Undifferentiated-Intersex).
- Race (Black or African American / American Indian or Alaska Native / Asian / Native Hawaiian or Other Pacific Islander / White /Other). If other, specify.
- Height (cm), weight (kg), Body Mass Index (kg / m²).

This information will be extracted from the Screening visit.

The demographics and other characteristics will be listed by subject (Screening visit).

Summary of the substance use will be summarized by placebo /dose-level cohort, and overall:

- Smoking status (Yes / No)
- If yes, smoking conditions (Current smoker/Quit before 3 months prior to Screening/ Quit after 3 months prior to Screening/ Missing)
- Was the subject screened for urine Drug abuse? (Yes / No)
- If yes, result (Positive/ Negative / Not determine)
- Was the subject screened for alcohol use? (Yes / No)
- If yes, result (Positive / Negative)

The smoking status will be extracted from the Screening visit.

The urine Drug abuse, and alcohol abuse will be extracted from the Baseline visit if available, otherwise will be extracted from the Screening visit.

The substance use will be listed by subject including the information reported in the screening and baseline visit.

5.4.1.2 Medical History

Medical history will be coded to Medical Dictionary for Regulatory Activities (MedDRA) terms. The version used will be specified in the data display footnote.

The medical history will be listed including the MedDRA codes, but not summarized.

5.4.1.3 Prior and Concomitant Medications

Prior and concomitant medications will be listed but not summarized.

5.4.2 Efficacy Analyses

The efficacy analysis will not be performed in this study.

5.4.3 Safety Analyses

The population used for safety analyses will be the Safety Analysis Set. No formal statistical hypothesis of the safety or tolerability are to be tested for this study.

Safety variables include adverse events, clinical laboratory values, 12-lead ECG, vital signs, and Physical Examination.

5.4.3.1 Treatment Exposure

Exposure of the ATL001 will be summarized by placebo / dose-level cohort. The following variables will be summarized:

- Number of doses administered per Subject.
- Subjects with any delayed dose.
- Subjects with any modified dose.
- Subjects with at least one skipped dose.
- Subjects who do not received any full dose administration.
- Compliance.

A listing of ATL001 administration information will be provided.

5.4.3.2 Adverse events

All AEs (TEAEs and non TEAEs) will be coded to System Organ Class (SOC) and Preferred Term (PT) using the MedDRA dictionary v25.1. or later.

The NCI-CTCAE version 5.0 or higher when available will be used to assess the severity grade of TEAEs.

5.4.3.2.1 TEAEs – Overview

An overall summary table will be provided showing the number of AEs/TEAEs (events), the number of subjects, and proportion of subjects who presented:

- Any AE.
- Any TEAE.
- Any TEAE grade 3 or higher.
- Any TEAE grade 3.
- Any TEAE grade 4.
- Any TEAE grade 5.
- Any TEAE related to ATL001.
- Any TEAE related to ATL001 grade 3 or higher.
- Any TEAE related to ATL001 grade 3.
- Any TEAE related to ATL001 grade 4.
- Any TEAE related to ATL001 grade 5.
- Any TEAE leading to temporary interruption of ATL001.
- Any TEAE leading to treatment permanent discontinuation of ATL001.
- Any Serious TEAE.
- Any Serious TEAE related to ATL001.
- Any Serious TEAE with a fatal outcome.
- Any Serious TEAE related to study discontinuation.
- Any Serious TEAE related to ATL001 with fatal outcome.
- Any AESI.
- Any AESI related to ATL001.

This information will be presented by placebo/ dose-level cohort, and overall.

5.4.3.2.2 TEAEs.

All AE summaries will be restricted to TEAEs only.

Treatment Emergent Adverse Events will be summarized:

- By worst grade according to National Cancer Institute Common Terminology Criteria for Adverse Events (NCI-CTAE version 5.0), per subject, using the latest version of MedDRA as event category.

The following tables will be created:

TEAEs: Worst grade by subject (by placebo / dose-level cohort, and overall):

- Incidence of TEAEs will be tabulated by Primary System Organ Class (SOC), Preferred Term (PT) and maximum CTCAE grade, showing the total incidence of SOC and PT within SOC.

TEAEs: More than 5 % of incidence (by placebo / dose-level cohort, and overall):

- Incidence of TEAEs with more than 5% of incidence will be tabulated by Preferred Term (PT).

TEAEs: Worst grade by subject related to (by placebo / dose-level cohort, and overall):

- Incidence of TEAEs related to ATL001 will be tabulated by SOC, PT and maximum CTCAE grade, showing the total incidence of SOC and PT within SOC.

Serious Adverse events: Worst grade by subject (by placebo / dose-level cohort, and overall)

- Incidence of SAEs will be tabulated by SOC, PT and cohort, showing the total incidence of SOC and PT within SOC and maximum CTCAE grade, showing the total incidence of SOC and PT within SOC.

A listing of AEs (Non TEAEs /TEAEs) will be sorted by placebo/ dose-level cohort, subject, Start Date, System organ class, and Preferred term.

5.4.3.3 Deaths

In case of death during the study period, it would be reported in the reasons for end of treatment and/or end of study.

5.4.3.4 Clinical Laboratory Test

To evaluate the safety profile the following laboratory tests will be performed:

- **Hematology**

- Hemoglobin
- Erythrocytes
- Leukocytes
- Neutrophils
- Lymphocytes
- Monocytes
- Eosinophils
- Basophils
- Ferritin
- C reactive protein (CRP)

- **Biochemistry**

- Alkaline phosphatase
- AST / SGOT
- ALT / SGPT
- Gamma-glutamyl transferase
- Creatinine
- Glucose
- Total Bilirubin
- Lactate dehydrogenase
- Triglycerides
- Calcium
- Chloride
- Potassium
- Sodium
- TSH
- BUN

- **Urinalysis**

- Quantitative
 - pH
 - Specific gravity
 - Microalbumin
 - Protein
- Qualitative
 - Urine bilirubin (Positive / Negative /Not Done)
 - Ketones (Positive / Negative /Not Done)
 - Nitrite (Positive / Negative /Not Done)
 - Occult blood (Positive / Negative /Not Done)
 - Acid Urate Crystals (Positive / Negative /Not Done)
 - Urine glucose (Positive / Negative /Not Done)
- Microscopic analysis quantitative (will be analyzed as qualitative)
 - RBC Casts (in range / above the range/ missing)
 - WBC Casts (in range / above the range/ missing)
- Microscopic analysis qualitative
 - Urine Appearance (Normal / Abnormal /Not Done)
 - Urine Color (Normal / Abnormal /Not Done)

For each parameter, summaries will be presented for the Screening, Baseline, and each scheduled post-baseline visit.

For each quantitative laboratory parameter, the values, and changes from baseline will be summarized by placebo / dose-level cohorts (including number of observations, missing, mean, SD, median, Q1, Q3, minimum, and maximum) will be calculated for each visit.

The decimal precision for each parameter will be based on the maximum number of decimals to which the results were reported on the eCRF.

If a result for a parameter that is normally considered quantitative is reported as a range (i.e., the result for basophils is reported as '<0.01'), this value will be not considered in the summary table. All the values reported will be included in the respective listing.

Lab Original results with ND/ NA/ NE/ UNK/ NQ/ UN etc: will not be evaluated or used for the analysis purpose.

All biochemistry, hematology, and urinalysis data will be listed.

The listings will be sorted by placebo /dose-level cohort, subject, parameter, visit and timepoint (if applicable).

The results and normal ranges will be displayed to the same decimal precision in the listings.

The clinically significant abnormal values will be flagged.

Notes:

- Clinical laboratory data will be analysed using standardized values.
- Only evaluable data will be used, and missing data will not be imputed.
- The Microscopic analysis quantitative parameters will be analysed as categorical variable.
- Biochemistry: FSH and Glomerular Filtration Rate will be shown in a listing.

Information on the derived variable Urea will be presented. The standardised values and changes from baseline will be summarised by placebo / dose level cohorts (including number of observations, missing, mean, SD, median, Q1, Q3, minimum and maximum) and will be calculated for each visit.

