		-	-	-

Date: 13 December 2023

Sponsor: Atlas Molecular Pharma S.L.

Study Code: ATL001-PI-CEP

NCT No.: 05647343

Category	Laboratory Parameter	Units		
		Conventional	SI	Site Laboratory
	Human Immunodeficiency Virus (HIV) antibody I and II COVID-19			

^{*}Only at Screening and/or Baseline (Day 1).

The observed values will be recorded in the eCRF and assessed as "normal" or "abnormal". Abnormal findings will be assessed as "clinically significant" or "not clinically significant".

Blood and urine samples will be collected at specific time points throughout the study. The timing of the assessments is described in Section 8.2.1 and and Table 1.

Details on collection, storage and handling of blood and urine samples will be provided in the respective Laboratory Manual.

Blood and Urine Volumes

The maximum amount of blood and urine to be collected for laboratory safety assessments (hematology, biochemistry, and urinalysis) along the study are 50 mL and 50 mL, respectively. For each day when a laboratory safety assessment sampling is collected, 5 mL of blood and 5 mL of urine will be withdrawn.

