13.1.4.2 Tolerability

Descriptive statistics will be calculated for the quantitative variables obtained in the vital signs records, ECG, physical examination and laboratory safety tests (hematology, biochemistry and urinalysis).

Vital Signs

Vital signs data will be presented by individual listings with flagging of abnormal values. Vitals signs data will be summarized by visit and treatment group, together with changes from baseline.

Electrocardiogram

Overall interpretation of ECG results (i.e., normal or abnormal) will be summarized. In addition, standard ECG parameters will be summarized by treatment group, together with changes from baseline.

Physical Examination

Physical examination data will be summarized by treatment group.

All abnormal physical findings will be listed.

Laboratory Safety Assessments

For laboratory data (hematology, biochemistry, and urinalysis), summary statistics will be produced for observed values and for changes from baseline to each visit. In addition, the number of abnormal and clinically significant observations will be tabulated for each treatment group by visit. Abnormal values will be flagged in listings.

Shift tables will be created for a subset of laboratory parameters, which will be defined in the SAP. Shift tables will show the number of subjects who changed from below, within or above the reference range at baseline to below, within or above the reference range at each time of assessment.

For laboratory values which are below the limit of quantification, the value corresponding to the limit of quantification will be used when summarizing data.

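### SAP 5.4.3.4 leaves out the laboratory abnormality counts and shift tables that Protocol 13.1.4.2 requires, reverses its rule for results below quantification, and SAP 2.4 records none of this

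*SAP*

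**What the plan says.** Protocol 13.1.4.2 (Laboratory Safety Assessments) asks for summary statistics and four further things:

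- Counts: "In addition, the number of abnormal and clinically significant observations will be tabulated for each treatment group by visit".
- Listing flags: "Abnormal values will be flagged in listings".
- Shift tables: "Shift tables will be created for a subset of laboratory parameters, which will be defined in the SAP". They are to cross the baseline category (below, within or above range) with the category at each assessment.
- Results below quantification: "the value corresponding to the limit of quantification will be used when summarizing data".

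SAP 5.4.3.4 delivers the summary statistics: "For each quantitative laboratory parameter, the values, and changes from baseline will be summarized by placebo / dose-level cohorts". The statistics named are n, missing, mean, SD, median, Q1, Q3, minimum and maximum at each visit. On listings it says "The clinically significant abnormal values will be flagged", and it prints normal ranges next to the results. For a quantitative result reported as an inequality, with basophils `<0.01` as its example, it says "this value will be not considered in the summary table".

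SAP 2.4 lists two modifications to Protocol v4.0: the added Screened population and the changed PK analysis set. SAP 5.4 keeps unscheduled and repeat assessments out of summary tables.

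**The concern.** The primary endpoint (Protocol 7) is an incidence, and clinically relevant changes in laboratory data are one of its components. Counts by dose group are the natural summary of an incidence. Under the SAP text, a blood-laboratory finding enters an incidence table only after it has been reported as an adverse event. Protocol 12.2 sets the bar for an asymptomatic finding: it must be judged clinically significant, meet the criteria for an SAE, or lead to discontinuation. Out-of-range values below that bar appear in no count by dose against pooled placebo, and nothing shows which subjects moved out of range from a normal baseline.

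The rule for low results works in the other direction from the protocol. Leaving them out lowers n and removes the bottom of the distribution, which can move the mean and the minimum upward.

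The shift subset is a separate matter. The protocol left that choice to the SAP. Cohorts 1 to 4 were analysed before Cohort 5 was enrolled (Protocol 13.4, SAP 5.4.6), so a subset chosen now is already partly after the fact, and more so the later it is chosen.

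**Working it through.** The plan gives no figure to reproduce here. The check compares the two texts and then asks what the planned statistics can still show.

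**1. Item by item**

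| Protocol 13.1.4.2 | SAP 5.4.3.4, blood parameters |
|---|---|
| Values and changes from baseline | Present |
| Abnormal and clinically significant counts by group and visit | Absent |
| Flag on abnormal values | Stated for clinically significant values only |
| Shift tables, subset named in the SAP | No table, no subset |
| Limit value for results below quantification | Reversed: result left out |

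SAP 2.4 records none of the last four rows.

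**2. Parameters affected.** SAP 5.4.3.4 lists 10 haematology and 15 biochemistry parameters: 10 + 15 = 25. Derived urea makes 26, also with continuous statistics only. The 4 quantitative urinalysis items (pH, specific gravity, microalbumin, protein) are treated in the same way. The categorical urinalysis items do get category counts. Parameters with an abnormal count or shift table: 0 of 25 blood and 0 of 4 quantitative urine. By comparison, SAP 5.4.3.5 gives a count of subjects with abnormal values for 4 of 4 vital signs, and SAP 5.4.3.6 for 6 of 6 ECG parameters.

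**3. What the by-visit statistics still show.** Take one visit, one common upper limit, no missing values and default SAS quartiles (an assumption). Each dose has 6 active subjects; pooled placebo has 5 × 2 = 10.

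- n = 6: Q1 is the 2nd ordered value, Q3 the 5th, and the median the mean of the 3rd and 4th. Checking maximum, Q3, median, Q1 and minimum in turn against the limit places the number above it at 0, 1, 2–3, 3–4, 5 or 6.
- n = 10: Q1 is the 3rd value, Q3 the 8th, and the median the mean of the 5th and 6th. The number above is placed at 0, 1–2, 3–5, 5–7, 8–9 or 10.

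A single high active subject is therefore visible at a visit, but 1 and 2 of 10 on placebo cannot be told apart. Baseline category and recurrence in the same subject are not visible at all. The limits themselves are promised only for the listings.

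**4. Counting by hand.** There are six post-dose panels: Day 1 at 2 h, Day 2, Day 5 at 2 h, Day 6, FU-V1 and FU-V2. Up to 25 × 6 × 40 = 6,000 listed values would have to be compared with their ranges.

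**5. Noise in restored counts.** If each of 25 independent parameters is out of range by chance with probability p, the share of subjects with at least one abnormal value at a visit is 1 − (1 − p)^25. This gives 22.2% at p = 0.01, 46.9% at p = 0.025 and 72.3% at p = 0.05. The values of p and independence are assumptions.

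**The case against.** The best reply is that the SAP may simply not restate the counts. Its introduction commits the contractors to the analyses described in the protocol, SAP 7 places table content in separate shells that are not public, and SAP 2.4 lists no laboratory change. On that reading the counts remain in force, and a statement that clinically significant values are flagged does not forbid flagging others. This has some force: the text does not show whether the counts were removed on purpose or left out. It cannot rescue the shift subset, which the protocol required in the SAP itself, or the rule for low results, which contradicts the protocol outright.

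Second, the endpoint concerns clinically relevant changes, and Protocol 12.2 makes clinically significant findings adverse events, which are tabulated by grade and dose group. That is correct, so the endpoint is not left unanalysed. What is missing is the count of abnormal and clinically significant observations that the protocol specified in addition.

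Third, Protocol 13.3 lets departures be recorded in an amendment, a revised SAP or the final report. Silence in SAP 2.4 is therefore not by itself a breach, but that section presents itself as the list of changes and is incomplete.

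Fourth, the planned mean and SD carry further information. For n = 6 the order statistics leave one unknown, which an SD printed with enough decimals can resolve. At the data's own precision it often cannot. For n = 10, five unknowns remain against two equations, so in general the bands stay.

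Finally, the study is descriptive with at most 40 subjects, and all values are listed. This limits the consequence but does not remove the discrepancy.

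**Conclusion.** The concern holds. For all 25 listed blood parameters the SAP text omits the counts and shift tables, states a narrower flag, and replaces the rule for results below quantification with its opposite, without recording any of it in SAP 2.4. The shift subset and the quantification rule are certain from the text alone. The missing counts are certain for the SAP as written, with the reservation that the table shells cannot be seen.

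This should be corrected, but the harm is limited. Values and ranges are in listings, extremes and quartiles are tabulated at each visit, and clinically significant findings reach the adverse event tables. No effect on dose-limiting toxicity or stopping decisions is claimed. How many abnormal or below-limit values occurred cannot be shown from the documents.

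**What to change.** In SAP 5.4.3.4:

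1. Restore counts of abnormal and of clinically significant observations by dose group, pooled placebo and visit.
2. Flag every abnormal value in the listings and mark the clinically significant ones separately.
3. Name the shift subset, for example ALT, AST, alkaline phosphatase, GGT, total bilirubin, creatinine, BUN, haemoglobin, leukocytes and neutrophils. The renal items fit the renal excretion described in Protocol 6.2.1.3.
4. Use the limit value for results below quantification, as the protocol says.

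Add one table that goes beyond the protocol, because by-visit counts do not give incidence per subject. It should show baseline category against worst post-dose category, with low and high directions separate and unscheduled and repeat values included, as subjects n (%) by dose group and pooled placebo. This needs a stated exception to SAP 5.4. CTCAE v5.0 grades could replace low/normal/high where limits exist.

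If any protocol item is dropped on purpose, SAP 2.4 should say so and why. The reporting rule in Protocol 12.2 stays as it is.

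The cost is one or two tables and a wider flag. No new data are needed. Protocol 11.4.6 states "The observed values will be recorded in the eCRF and assessed as" normal or abnormal, with abnormal findings further classed by clinical significance. The drawback is trivial flags, so the counts should be read per parameter, against baseline and pooled placebo, and not as any abnormality across the panel.

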5.4.3.7 Physical Examination

All subjects will undergo a standard physical examination. General physical examinations will include the following body systems:

Heent, dermatological, psychiatric, neurological, cardiovascular, respiratory system, renal, abdominal and gastrointestinal, genitourinary, musculoskeletal, endocrine and metabolic, hematological and lymphatic, allergies and drug sensitivities, others.

The examinations will be recorded and assessed as “normal” or “abnormal”. Abnormal findings will be assessed as “clinically significant” or “not clinically significant”.

Any clinically significant abnormalities will be recorded either as medical history or concomitant disease (if detected at screening) or as adverse event.

Data from physical examinations will be listed. The listing will be sorted by placebo /dose-level cohort, subject, parameter, visit, and timepoint (if applicable).

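### The SAP departs from protocol 13.1.4.2 on laboratory, ECG and physical examination outputs without declaring it, including a reversed below-limit rule; separately and minor, its partial-date rule can misclass post-dose AEs

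*SAP*

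**What the plan says.** **Protocol 13.1.4.2 (Tolerability).**

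- For haematology, biochemistry and urinalysis, "the number of abnormal and clinically significant observations will be tabulated for each treatment group by visit".
- "Shift tables will be created for a subset of laboratory parameters, which will be defined in the SAP".
- For laboratory results below the limit of quantification, "the value corresponding to the limit of quantification will be used when summarizing data".
- All abnormal laboratory values are to be flagged in the listings.
- The overall ECG reading, normal or abnormal, is to be summarised.
- "Physical examination data will be summarized by treatment group".

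**SAP.** Section 5.4.3.4 gives descriptive statistics and changes from baseline for quantitative laboratory parameters, and categories for qualitative urinalysis. On abnormality it says "The clinically significant abnormal values will be flagged". Where a normally quantitative result arrives as a range, with <0.01 as the example, "this value will be not considered in the summary table". Section 5.4.3.6 puts the overall ECG interpretation in a listing. Section 5.4.3.7 says "Data from physical examinations will be listed" and specifies no table.

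SAP 2.4, which sets out the changes from protocol v4.0, names two: the added Screened population and the redefined PK set.

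**AE onset dates (SAP 5.4.8).** A missing day becomes the 1st of the recorded month. A missing day and month become 1 January 2023. If the result is incoherent with the subject's other dates, the day is taken from those dates. A partly dated AE that is related to medication is a TEAE. The SAP adds that it does not expect partial dates to occur.

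**The concern.** The primary endpoint (protocol 7) is the incidence of AEs and of clinically relevant changes in vital signs, ECG, physical examination and laboratory data. Incidence needs counts. The SAP counts subjects with abnormal vital signs and ECG parameters (5.4.3.5, 5.4.3.6), but it specifies no such count for quantitative laboratory data and no summary at all for physical examination.

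The below-limit rule is more than missing detail: the two documents give opposite instructions for the same data, and the SAP's version shifts the mean in a known direction. Because SAP 2.4 is silent, a reader would take the protocol's laboratory, ECG and examination analyses to be unchanged.

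The date rule raises a smaller question: whether an AE that began after dosing can drop out of the treatment-emergent tables.

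**Working it through.** The plan gives no figure on this point to reproduce, so the check compares the texts and adds short arithmetic.

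**1. Item by item**

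| Protocol 13.1.4.2 | SAP text | Declared in SAP 2.4 |
|---|---|---|
| Abnormal laboratory counts | Not specified for quantitative parameters; qualitative urinalysis has categories | No |
| Clinically significant laboratory counts | Not specified; flagged in listings | No |
| Shift tables, subset set by the SAP | No shift table, no subset | No |
| Below-limit results at the limit | Left out of summaries | No |
| All abnormal laboratory values flagged | Clinically significant ones only | No |
| ECG overall interpretation summarised | Listed | No |
| Physical examination summarised | Listed | No |

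The general statement in SAP 5.4 that applicable data will be summarised names none of these outputs, and 5.4.3.4 to 5.4.3.7 are the specific text.

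**2. Extent.** SAP 5.4.3.4 lists 10 haematology, 15 biochemistry and 4 quantitative urinalysis parameters (pH, specific gravity, microalbumin, protein): 10 + 15 + 4 = 29 without an abnormal count. A dose group has 6 subjects. The pooled placebo group (SAP 4.1) has 5 × 2 = 10. One subject is therefore 1/6 = 16.7 or 1/10 = 10 percentage points.

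**3. Below-limit rule.** Let k of n subjects fall below the limit L, and let the others average rL with r ≥ 1.

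- SAP mean = rL, on n − k subjects.
- Protocol mean = [(n − k)rL + kL]/n, on n subjects.
- Difference = kL(r − 1)/n, which is never negative.

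The true values of the k subjects lie below L, so the protocol mean is itself no lower than the true mean. The SAP mean lies further out in the same direction. With one of 6 subjects below the limit, n falls from 6 to 5 and the mean rises by L(r − 1)/6. No document gives k, r or L for any laboratory parameter, so the size cannot be stated.

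SAP 4.1 sets a change from baseline to missing if either value is missing. The SAP does not say whether an excluded result counts as missing. If it does, a subject below the limit at baseline leaves the change summary at every visit.

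**4. Partial AE dates.** Example: consent 20 April, first dose 15 May, true onset 20 May, day not recorded.

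- The imputed onset is 1 May. It is before first dose, so the AE is non-TEAE.
- It is after consent, so nothing in those dates triggers the coherence clause.
- If the AE is judged not related, it leaves the TEAE tables. It stays in the overview row for any AE and in the listing (SAP 5.4.3.2).

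How often this could happen, given a missing day and a not-related AE, was enumerated over 731 consecutive first-dose dates and onsets on Days 1 to 35, all equally likely. This gives the share of imputed dates that fall between consent and first dose:

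| Consent before first dose | Share |
|---|---|
| 1 day | 2.8% |
| 7 days | 17.4% |
| 14 days | 30.2% |
| 30 days | 42.1% |

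Hand check for 7 days, with an average month of 30.4375 days: (7 × 30.4375 − 28)/(35 × 30.4375) = 185.06/1065.31 = 17.4%. These are upper limits, because other recorded dates may trigger the coherence clause. They are not expected error rates.

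For a year-only onset in Cohort 5, 1 January 2023 is 346 days before 13 December 2023, the date of the protocol version that added that cohort. The imputed date is incoherent for every such subject. The class then rests wholly on a clause that names no target date.

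**The case against.** A reader might infer that clinically relevant laboratory and examination changes will go uncounted, so that the primary endpoint cannot be analysed. The documents do not support that. Under protocol 12.2 an asymptomatic laboratory abnormality is reported as an AE if it is clinically significant. Under SAP 5.4.3.7 clinically significant examination findings after screening become AEs. Most such changes therefore reach the AE tables by group. What remains for laboratory data is a result accompanied by symptoms: the symptom is the AE and the result is supporting information.

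All laboratory values are listed with normal ranges, and all examinations are listed, for at most 40 subjects in a descriptive trial with no hypothesis test.

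A reader might also infer that the tables will not be produced, or that silence in SAP 2.4 is itself a breach. Neither follows. SAP 7 refers table content to separate shells, which were not available and may contain some of these outputs. Protocol 13.3 lets a deviation be justified in an amendment, a revised SAP or the final report. But the protocol assigns the shift-table subset to the SAP itself, and shells would not remove the written conflict on below-limit results or flagging.

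On dates, AEs are recorded daily in a diary and partial dates are not expected. Related AEs are protected, and SAP 4.5.2 counts missing or unknown causality as related. The rule cannot hide an AE judged drug-related, and it should add no weight to the main point.

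**Conclusion.** The point holds as an undeclared departure of SAP 5.4.3.4, 5.4.3.6 and 5.4.3.7 from protocol 13.1.4.2. The below-limit exclusion contradicts the protocol and biases laboratory means upward by an unknown amount. Any percentage put on it would rest on invented inputs. The other items are outputs that the SAP text omits or narrows. They should be corrected because the endpoint is an incidence and the protocol asked for the counts, but the practical loss is limited by AE reporting and full listings. The conclusion concerns the SAP text only and depends on the unseen shells for what is finally produced.

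The date rule is a real but minor defect. It reaches only not-related AEs with incomplete onset dates.

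**What to change.** **Laboratory, ECG and physical examination.** In SAP 5.4.3.4:

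- summarise below-limit laboratory results at the limit of quantification;
- add abnormal and clinically significant counts by group and visit for haematology, biochemistry and urinalysis, including the four quantitative urinalysis parameters;
- name the shift-table parameters;
- flag all abnormal values.

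In 5.4.3.6 and 5.4.3.7, summarise the ECG overall interpretation and the physical examination by group. Otherwise, declare and justify each departure in SAP 2.4. The cost is one SAP amendment and a few tables. The normal/abnormal and clinical-significance assessments are already recorded (protocol 11.4.3, 11.4.5, 11.4.6).

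**Partial dates.** In SAP 5.4.8, class a partly dated AE as a TEAE unless its known onset parts or its stop date show that it began (without later worsening) or ended before first dose. Keep the existing rules that related partly dated AEs, and pre-existing AEs that worsen after dosing, are TEAEs. Delete the fixed 1 January 2023 date.

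The cost is that some pre-dose AEs will be called TEAEs. With uniform dates and no known stop date, this is up to 1 − 15.5/30.4375 = 49% of day-missing onsets in the 30 days before dosing. If the AE is known to have ended 1, 3, 7 or 14 days after onset, it falls to 3%, 9%, 20% or 35%. Few AEs should be affected, since partial dates are expected to be rare.
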